APPENDIX B. INFORMATION REGARDING EFFECTIVENESS OF CONTRACEPTIVE METHODS

For male participants in the study:

Male participants should use a condom during treatment through 90 days after the end of systemic exposure. If the male participant has a partner that is of child-bearing potential, the partner should also use contraception through 90 days after the end of relevant systemic exposure. In addition, male participants must refrain from donating sperm during the study through 90 days after the end of relevant systemic exposure. Males who have had a vasectomy qualify as having met the requirement for a highly effective birth control method.

For female participants in the study:

The following methods that can achieve a failure rate of less than 1% per year when used consistently and correctly are considered as highly effective birth control methods:

- Combined (estrogen and progestogen containing) hormonal contraception associated with inhibition of ovulation
 - oral
 - intravaginal
 - transdermal
- Progestogen-only hormonal contraception associated with inhibition of ovulation
 - oral
 - injectable
 - implantable^a
- Intrauterine device^a
- Intrauterine hormone-releasing system^a
- Bilateral tubal occlusion^a
- Vasectomized partner^{a,b}
- Sexual abstinence^c

Acceptable birth control methods that result in a failure rate of more than 1% per year include:^d

- Progestogen-only oral hormonal contraception, where inhibition of ovulation is not the primary mode of action
- Male or female condom with or without spermicide^e
- Cap, diaphragm, or sponge with spermicide^e
- Tubal ligation

Source: Clinical Trial Facilitation and Coordination Group 2014.

^a Contraception methods that in the context of this guidance are considered to have low user dependency.

^b Vasectomized partner is a highly effective method of avoiding pregnancy provided that partner is the sole sexual partner of the woman of childbearing potential study participant and that the vasectomized partner has received medical assessment of the surgical success.

^c In the context of this guidance, sexual abstinence is considered a highly effective method only if defined as refraining from heterosexual intercourse during the entire period of risk associated with the study treatments. The reliability of sexual abstinence needs to be evaluated in relation to the duration of the clinical study and the preferred and usual lifestyle of the participant.

^d Choices are for US and Canada participants only and include above less than 1% failure rate methods.

^e A combination of male condom with either cap, diaphragm, or sponge with spermicide (double barrier methods) are also considered acceptable, but not highly effective, birth control methods.

APPENDIX C. WHO CLASSIFICATION OF TOPICAL CORTICOSTEROIDS

Hydrocortisone and betamethasone are examples of low- and high-potency topical corticosteroids. Topical corticosteroids have been ranked in terms of potency into 4 groups consisting of 7 classes. Class I topical corticosteroids are the most potent, and Class VII are the least potent. Efficacy and side-effects are greatest with the Class I ultra-high-potency preparations, which should only be used for limited time periods (2-3 weeks). Representative preparations by group are listed in the table below. These groups may vary depending on the formulation and concentration and should be considered approximate. In general, ointments are more potent than creams or lotions. Potency is also increased when topical corticosteroids are used under occlusive dressings or in intertriginous areas.

Potency	Class	Topical Corticosteroid	Formulation
Ultra high I		Clobetasol propionate	Cream, 0.05%
		Diflorasone diacetate	Ointment, 0.05%
High II		Amcinonide	Ointment, 0.1%
		Betamethasone dipropionate	Ointment, 0.05%
		Desoximetasone	Cream or ointment, 0.025%
		Fluocinonide	Cream, ointment or gel, 0.05%
		Halcinonide	Cream, 0.1%
	III	Betamethasone dipropionate	Cream, 0.05%
		Betamethasone valerate	Ointment, 0.1%
		Diflorasone diacetate	Cream, 0.05%
		Triamcinolone acetonide	Ointment, 0.1%
Moderate IV	IV	Desoximetasone	Cream, 0.05%
		Fluocinolone acetonide	Ointment, 0.025%
		Fludroxycortide	Ointment, 0.05%
		Hydrocortisone valerate	Ointment, 0.2%
		Triamcinolone acetonide	Cream, 0.1%
	V	Betamethasone dipropionate	Lotion, 0.02%
		Betamethasone valerate	Cream, 0.1%
		Fluocinolone acetonide	Cream, 0.025%
		Fludroxycortide	Cream, 0.05%
		Hydrocortisone butyrate	Cream, 0.1%
		Hydrocortisone valerate	Cream, 0.2%
		Triamcinolone acetonide	Lotion, 0.1%
Low	VI	Betamethasone valerate	Lotion, 0.05%
		Desonide	Cream, 0.05%
		Fluocinolone acetonide	Solution, 0.01%
	VII	Dexamethasone sodium phosphate	Cream, 0.1%
		Hydrocortisone acetate	Cream, 1%
		Methylprednisolone acetate	Cream, 0.25%

Source: WHO 1997.

APPENDIX D. COVID-19 PANDEMIC MITIGATION STRATEGIES AND INSTRUCTIONS

The COVID-19 global pandemic presents numerous challenges to the ongoing conduct of clinical trials. In line with the European Medicines Agency Guidelines on the Management of Clinical Trials During the COVID-19 (Coronavirus) Pandemic (2020), the sponsor has issued the following Protocol considerations to ensure participant safety is maintained and adequate benefit/risk analyses are applied relative to the completion of study procedures and maintaining the investigational product supply chain.

Recognizing the flexibility required to manage the impact of the pandemic on this clinical trial, additional details will be added to respective study manuals and project plan documents and communicated to the investigative sites as needed.

Study Site Visits

If local travel restrictions, isolation requirements, or the investigator's benefit/risk assessment determines it to be unsafe for participants to attend study visits at the investigational site, the site staff may elect to pursue the following:

- In order to minimize participant risk, study visits (except Week 52 and Week 104 visits) may be conducted via telemedicine modalities (phone or video). At a minimum, a review of AEs, concomitant medications, and study drug compliance must be completed. Periodic on-site visits should be conducted whenever feasible. The physician efficacy assessments must not be conducted by phone or video.
- Week 52 and Week 104 Visits must be conducted in person in their entirety because VASI assessments must be completed by the qualified raters face to face. These visits cannot be missed or conducted remotely. The investigator should document the visit window deviation in the eCRF if necessary.

Investigational Medicinal Product Dispensation and Distribution

In order to ensure the continuity of providing their participants' clinical supplies within the constraints imparted by the pandemic, the site staff can decide to supply study drug to participants. Adequate supplies of study drug as determined by the investigator to cover 12 weeks can be shipped to the participants by the investigator or appropriately delegated staff (eg, the study pharmacy staff) using a third-party service if duly authorized by the participant. The study site may use their own preferred courier, provided the courier adheres to certain standards (eg, use of personal protection equipment, maintenance of temperature-controlled transit environment) or one centrally contracted by the sponsor.

Clinical Trial Monitoring

Study monitoring visits may be postponed; however, the site monitor will continue to employ off-site monitoring practices such as routine communication methods (eg, phone calls, emails, video visits) with the sites to get information on trial progress, participant status, and information on issue resolution. The study monitor may remotely review data entered into the EDC for accuracy and completeness. Remote source data verification may be implemented with agreement of the principal investigator and institution, as applicable.

If the study site monitor cannot be on-site to perform the final drug accountability for reconciliation purposes, and the operation cannot be postponed, it may be performed by a pharmacist from the hospital pharmacy or by the study coordinator/data manager with suitable training. The study drug can be returned to the sponsor by the hospital pharmacy directly, or it can be destroyed in accordance with local practices, if applicable, and with sponsor approval.

APPENDIX E. PROTOCOL AMENDMENT SUMMARY OF CHANGES

Document	Date	
Amendment 1:	28 SEP 2020	
Amendment 2:	10 NOV 2020	

Amendment 2 (10 NOV 2020)

Overall Rationale for the Amendment:

The main purpose of this amendment is to add language to the Protocol to inform sites of alternative strategies to guarantee continuity of the clinical trial conduct and oversight in response to the COVID-19 pandemic.

1. Appendix D, COVID-19 Pandemic Mitigation Strategies and Instructions

Description of change: Added Appendix D to the Protocol and added cross-references to the appendix to relevant sections.

Rationale for change: To provide sites with Protocol-related guidance in response to the COVID-19 pandemic.

2. **Incorporation of administrative changes.** Other minor, administrative changes and clarifications have been incorporated throughout the Protocol and are noted in the redline version of the amendment.

Amendment 1 (28 SEP 2020)

Overall Rationale for the Amendment: The primary purpose of this amendment is to accommodate the EMA PDCO recommendation regarding the DLQI/CDLQI endpoint and to align the PK endpoints with those of parent studies INCB 18424-306 and INCB 18424 307.

1. Title Page; Section 1, Protocol Summary

Description of change: Added TRuE-V LTE to the Protocol title.

Rationale for change: To include the short name in the title.

2. Section 1, Protocol Summary (Table 1: Primary and secondary Objectives and Endpoints); Section 3, Objectives and Endpoints (Table 8: Objectives and Endpoints)

Description of change: Moved endpoint for DLQI/CDLQI from exploratory to secondary.

Rationale for changes: To address EMA PDCO recommendation.

2. Section 1, Protocol Summary (Table 1: Primary and Secondary Objectives and Endpoints); Section 3, Objectives and Endpoints (Table 8: Objectives and Endpoints)

Description of change: Moved endpoint for PK from exploratory to secondary.

Rationale for change: To align with INCB 18424-306 and INCB 18424-307 parent studies.

3. Section 1, Protocol Summary (Table 3: Schedule of Activities); Section 8.4, Pharmacokinetic Assessments

Description of change: Added clarifications that PK samples should be collected at predose and the time of the last study drug application is to be recorded in the eCRF.

Rationale for change: To align PK sample collection procedures with INCB 18424-306 and INCB 18424-307 parent studies.

4. Section 5.1, Inclusion Criteria (Inclusion Criteria 5a and 6)

| Abbreviation | Term | |
|----------------|---|--|
| T-VASI | total body Vitiligo Area Scoring Index | |
| T-VASI50/75/90 | ≥ 50%/75%/90% improvement in total body Vitiligo Area Scoring Index | |
| VASI | Vitiligo Area Scoring Index | |
| | | |
| VNS | Vitiligo Noticeability Scale | |
| WHO | World Health Organization | |
| | | |

1. INTRODUCTION

This is a Phase 3, double-blind, vehicle-controlled, randomized withdrawal and treatment extension study that will enroll eligible participants who have completed either Study INCB 18424-306 or Study INCB 18424-307 (parent studies) in which the participants will have been using ruxolitinib cream 1.5% BID for the previous 28 to 52 weeks (depending on their initial randomization in the parent study). Participants who successfully completed either of the parent studies and tolerated ruxolitinib cream treatment without a safety concern and with good compliance for continuation may be eligible to participate in this treatment extension study.

Eligible participants in this treatment extension study will be assigned to 1 of 2 cohorts, Cohort A or Cohort B, based on their F-VASI responses at the time of enrollment in this extension study (ie, at Week 52). Participants who achieved complete or almost complete facial repigmentation (ie, achieved \geq F-VASI90) at Week 52 in the parent study will be assigned to Cohort A, stratified by the original treatment received on study Day 1 of the parent study, and randomized 1:1 to treatment with vehicle cream BID or ruxolitinib cream 1.5% BID for an additional 52 weeks (ie, until EOT or at Week 104). However, any participant in Cohort A who experiences relapse (defined as \leq F-VASI75) will receive ruxolitinib cream 1.5% BID as an open-label rescue treatment until they complete treatment (Week 104 or EOT). Participants who did not achieve \geq F-VASI90 at Week 52 of the parent studies will be assigned to Cohort B and will continue ruxolitinib cream 1.5% BID for up to 52 weeks (ie, EOT or Week 104).

The purpose of this SAP is to provide details of the statistical analyses that have been outlined in the study Protocol. The scope of this plan will be executed by the Department of Biostatistics or designee, and the analyses of PK will be executed by the Department of Clinical Pharmacokinetics or designee.

2. STUDY INFORMATION, OBJECTIVES, AND ENDPOINTS

2.1. Protocol and Case Report Form Version

This SAP is based on INCB 18424-308 Protocol (Amendment 2 dated 10 NOV 2020) and INCB 18424-308 CRF approved 01 DEC 2020. Unless superseded by an amendment, this SAP will be effective for all subsequent Protocol amendments and CRF versions.

[figure not shown]
2.2. Study Objectives and Endpoints

Table 1 presents the endpoints and objectives.

Table 1: Objectives and Endpoints

| Objectives | Endpoints |
|---|--|
| Primary | • |
| To evaluate the duration of clinical response of ruxolitinib cream in participants with vitiligo. | For participants who are randomized in Cohort A: • Time to relapse (defined as < F-VASI75). |
| Key Secondary | |
| To evaluate the duration of clinical response of ruxolitinib cream in participants with vitiligo. | For participants who are randomized in Cohort A: • Time to maintain ≥ F-VASI90 response. |
| Secondary | |
| To further evaluate the efficacy of ruxolitinib cream. | Proportion of participants who achieve F-VASI50/75/90 during the extension treatment period. Actual measurements, change, and percentage change from baseline in F-VASI. Proportion of participants who achieve T-VASI50/75/90 during the extension treatment period. Actual measurements, change, and percentage change from baseline in T-VASI. Actual measurements, change, and percentage change from baseline in F-BSA. Actual measurements, change, and percentage change from baseline in T-BSA. Proportion of participants achieving a VNS of "4 – A lot less noticeable" or "5 – No longer noticeable" during the extension treatment period. |
| To determine the participants' quality of life. | Change from Week 52 in DLQI (or CDLQI) during the extension treatment period. |
| To evaluate the safety and tolerability of ruxolitinib cream. | The frequency and severity of AEs; includes performing physical examinations and collecting vital signs and laboratory data for hematology and serum chemistry. |
| To evaluate the ruxolitinib PK in plasma after treatment with ruxolitinib cream. | Trough plasma concentrations of ruxolitinib at Week 80 and Week 104. |

Table 1: Objectives and Endpoints (Continued)

3. STUDY DESIGN

This is a Phase 3, double-blind, vehicle-controlled, randomized withdrawal and treatment extension study that will enroll eligible participants who have completed either Study INCB 18424-306 or Study INCB 18424-307 (parent studies) in which the participants will have been using ruxolitinib cream 1.5% BID for the previous 28 to 52 weeks (depending on their initial randomization in the parent study; see Figure 1).

The parent studies are randomized, vehicle-controlled studies in adolescent and adult participants (age \geq 12 years) with nonsegmental vitiligo who have depigmented areas including \geq 0.5% BSA on the face, \geq 0.5 F-VASI, \geq 3% BSA on nonfacial areas, and \geq 3 T-VASI. Total body involved vitiligo area (facial and nonfacial) was not to exceed 10% BSA. In each parent study, approximately 300 participants were to be randomized 2:1 to receive an initial, double-blind study treatment of ruxolitinib cream 1.5% BID or vehicle cream BID (applied to depigmented vitiligo areas on the face and body up to 10% total BSA) for 24 weeks. After completion of the Week 24 assessments, participants in these studies were offered the opportunity to receive an additional 28 weeks of open-label treatment extension with ruxolitinib cream 1.5% BID under the parent study protocol.

Participants who successfully completed the 52-week treatment in either of the parent studies (ie, 52 weeks of ruxolitinib cream or 24 weeks of vehicle cream plus 28 weeks of ruxolitinib cream) and tolerated ruxolitinib cream treatment without safety concern and with good compliance for continuation may be eligible to participate in this treatment extension study.

[figure not shown]
Visits in this treatment extension study are named to reflect continuation from the parent studies, with the first visit of this treatment extension study occurring at Week 52. The eligibility assessment for this extension study occurs at Week 52. The treatment extension period of this study comprises the period from the Week 52 visit to the Week 104 visit (inclusive). Following the last application of study treatment at Week 104, there will be a 30-day safety follow-up period to evaluate safety and duration of response.

Eligible participants in this study will be assigned to 1 of 2 cohorts, Cohort A or Cohort B, based on their F-VASI responses at the time of enrollment in this study (ie, at Week 52).

Treatment in Cohort A is a randomized withdrawal design and will provide data on the duration of response following withdrawal of ruxolitinib cream and maintenance of response with its continued use. Participants who achieve complete or almost complete facial repigmentation (ie, achieve ≥ F-VASI90) at Week 52 in the parent study will be assigned to Cohort A and will be stratified by the original treatment received on study Day 1 of the parent study and randomized 1:1 to treatment with vehicle cream BID or ruxolitinib cream 1.5% BID for an additional 52 weeks (ie, until EOT at Week 104). However, any participants in Cohort A who experience relapse (defined as < F-VASI75) will receive ruxolitinib cream 1.5% BID as an open-label rescue treatment until they complete treatment (Week 104 or EOT).

Treatment in Cohort B will provide long-term efficacy and safety data for ruxolitinib cream in participants with vitiligo. Participants who did not achieve ≥ F-VASI90 at Week 52 of the parent studies will be assigned to Cohort B and will continue ruxolitinib cream 1.5% BID for 52 weeks (ie, until EOT Week 104).

Figure 1: Study Design Schema

¹ All participants in Cohort A will use their randomly assigned treatment (either vehicle or ruxolitinib cream) on both the face and total body.

3.1. Randomization

All participants will be centrally assigned to study treatment using an IRT system. For Cohort A, the system will assign in a 1:1 ratio (ruxolitinib cream 1.5% BID/vehicle). For Cohort B, the system will assign all participants to ruxolitinib cream 1.5% BID.

3.2. Control of Type I Error

All statistical analyses are exploratory in nature. No alpha control will be implemented. Unless otherwise specified, all CIs provided will be at the 95% confidence level.

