6.3. Measures to Minimize Bias: Randomization and Blinding

All participants will be centrally assigned to study treatment using an IRT system. For Cohort A, the system will assign in a 1:1 ratio (ruxolitinib cream 1.5% BID:vehicle). For Cohort B, the system will assign all participants to ruxolitinib cream 1.5% BID.

The IRT will track participant visits, randomize participants according to the defined parameters, maintain the blinding (Cohort A only), and manage study drug inventory. Full details will be provided in the IRT Manual. Study treatment will be dispensed at the study visits summarized in the SoA (see Table 3).

For Cohort A, the participant, investigator, and sponsor will remain blinded to treatment assignment; the treatment for Cohort B will be open-label. After the database lock for the primary analysis (Week 104), the participant, the investigator, and the sponsor will be unblinded.

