10.3. Level of Significance

The primary and key secondary endpoints will be tested in a fixed sequence at 2-sided $\alpha = 0.05$ level, that is, the key secondary endpoint will be tested only if the primary is rejected. No formal statistical tests will be performed for other endpoints. All confidence intervals will be 95%.

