7.3.1. Primary Efficacy Analysis

The primary analysis will be based on the ITT-Ext population (defined as achieving ≥ F-VASI90 at Week 52). Relapse, a binary variable event, is defined as a loss of F-VASI75 response assessed as percentage improvement from baseline (Day 1 of the parent study) to F-VASI < 75%. The time to relapse is defined as the number of days from the Week 52 randomization date to the first evaluation date at which the participant meets the definition of relapse. For participants who discontinue early, complete the study without meeting criteria for the event, or received open-label rescue treatment (1.5% BID) without meeting the criteria for the event, the time to event will be censored at the last assessment date or the date of rescue treatment. Details of the censoring and missing data handling are provided in Table 2. The time-to-event data will be assessed using the Kaplan-Meier product limit method. Treatment comparisons between ruxolitinib 1.5% cream BID and vehicle cream BID will be performed using the log-rank test. Hazard ratios and the corresponding 95% CIs will be estimated using the Cox proportional hazards model. This model will include the treatment group (1.5% BID and vehicle) and stratification factors (skin type and region).

The incidence of relapse will be summarized by ruxolitinib cream 1.5% BID and vehicle at each timepoint. Swimmer plots will be provided for the time to relapse and subgroup swimmer plots by baseline characteristics, such as age group and duration of disease, will be provided.

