7.4. Analysis of the Key Secondary Efficacy Parameters

The key secondary endpoint will be analyzed using the ITT-Ext population.

The key secondary endpoint will be the time to maintain \geq F-VASI90 response. For F-VASI90 response, a categorical variable event is defined to be equal to 1 (Yes) when the improvement from baseline in F-VASI is \geq 90% and 0 (No) if < 90%. The time to maintain \geq F-VASI90 response is defined as the number of days from the Week 52 randomization to the first evaluation date at which the participant has percentage change from baseline in F-VASI < 90%.

The statistical comparisons and censoring and missing data handling for the key secondary endpoint will be analyzed using a similar method as specified in the primary analysis.

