10. CHANGES AND MODIFICATIONS TO THE ANALYSIS PLAN

All versions of the SAP are listed in Table 8.

Table 8: Statistical Analysis Plan Versions

| SAP Version | Date |
|-------------|-------------|
| Original | 06 OCT 2022 |

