10.1. Changes to Protocol-Defined Analyses

The data from participants at Site 710 were removed from all efficacy analyses performed on the ITT-Ext population and FAS for the final CSR owing to noncompliance with the Protocol in the parent study resulting in serious concerns with the data quality. Data from participants at Site 710 were included in all other analyses because all participants at Site 710 applied study drug at least once.

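### SAP 3.2 drops the protocol's fixed-sequence test of the primary and key secondary endpoints, and SAP 10.1 does not record the change

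*SAP*

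**What the plan says.** Protocol 10.3 (Level of Significance) sets a two-step fixed sequence at two-sided 0.05. Time to relapse comes first, and "the key secondary endpoint will be tested only if the primary is rejected". All remaining endpoints are excluded from formal testing.

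The SAP ties itself to that version of the protocol in section 2.1: "This SAP is based on INCB 18424-308 Protocol (Amendment 2 dated 10 NOV 2020". Its section 3.2 (Control of Type I Error) then says: "All statistical analyses are exploratory in nature. No alpha control will be implemented".

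The SAP still treats the two endpoints as the protocol does. Section 7.3.1 plans for the primary: "Treatment comparisons between ruxolitinib 1.5% cream BID and vehicle cream BID will be performed using the log-rank test". Section 7.4 says that the comparisons for the key secondary "will be analyzed using a similar method as specified in the primary analysis". Neither section gives a significance level, a testing order or a gate.

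SAP 10.1 (Changes to Protocol-Defined Analyses) has one entry: "The data from participants at Site 710 were removed from all efficacy analyses performed on the ITT-Ext population", together with the FAS. It does not mention alpha or testing order. SAP 10.2 reads as not applicable, but it concerns changes between SAP versions, and Table 8 lists only the original of 06 OCT 2022.

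**The concern.** The protocol makes the Cohort A comparison a formal test with a protected second step. The SAP makes it exploratory with no protection. A reader holding both documents cannot tell whether a log-rank p-value below 0.05 for relapse supports a claim, or whether the F-VASI90 result may be interpreted if relapse fails.

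The key secondary has most to lose, because the gate was its only safeguard. The primary loses its stated confirmatory status but not its own 5% error rate.

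The silence in SAP 10.1 adds a second problem. Protocol 6.3 says: "After the database lock for the primary analysis (Week 104), the participant, the investigator, and the sponsor will be unblinded". Because the change is neither recorded nor dated, the documents do not show whether the testing rule was dropped before or after treatment assignments were known.

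**Working it through.** **Step 1. Set the rules side by side.**

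| Item | Protocol Amendment 2 | SAP, 06 OCT 2022 |
|---|---|---|
| Status of primary and key secondary | Formally tested (10.3) | Exploratory, like everything else (3.2) |
| Alpha | Two-sided 0.05 (10.3) | None stated |
| Order and gate | Primary, then key secondary if the primary is rejected (10.3) | None (3.2, 7.3.1, 7.4) |
| Comparison | Log-rank for both (10.4.1) | Log-rank for the primary (7.3.1), similar method for the key secondary (7.4) |
| Power calculation | None (10.1) | None (3.3) |
| Change recorded | – | Site 710 only (10.1) |

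The rules in the first three rows conflict, and no section of either document reconciles them.

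**Step 2. Reproduce the protocol's 5%.** Let H1 be the null for relapse and H2 the null for F-VASI90, each tested at 0.05.

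- If H1 is true, any false rejection requires rejecting H1, so the family-wise error is 0.05.
- If H1 is false and H2 is true, the only possible false rejection is H2, and it requires rejecting both, so the error is at most 0.05. With independent tests and 80% power for H1 it is 0.80 × 0.05 = 0.04.

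A simulation of bivariate normal statistics under both nulls (2,000,000 draws per correlation) gave 0.0498 to 0.0501. The protocol's figure is reproduced.

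**Step 3. Remove the gate.** This step assumes that someone reads both p-values at 0.05; the SAP sets no such threshold. With both nulls true and correlation ρ between the test statistics:

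FWER = P(|Z1| > 1.96 or |Z2| > 1.96) = 1 − P(|Z1| ≤ 1.96 and |Z2| ≤ 1.96)

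At ρ = 0 this is 1 − 0.95² = 0.0975. At ρ = 1 the two tests coincide and it is 0.05. The excess over 0.05 is the probability that the key secondary gives p < 0.05 while the primary does not, which is the event the gate blocks.

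| ρ (assumed) | FWER, no gate | Excess over 5% |
|---|---|---|
| 0 | 9.75% | 4.75 points |
| 0.3 | 9.51% | 4.51 |
| 0.5 | 9.07% | 4.07 |
| 0.7 | 8.35% | 3.35 |
| 0.8 | 7.81% | 2.81 |
| 0.9 | 7.04% | 2.04 |
| 0.95 | 6.46% | 1.46 |
| 0.99 | 5.66% | 0.66 |
| 1 | 5.00% | 0 |

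The same simulation, run ungated at ρ = 0, 0.3, 0.5, 0.7, 0.9 and 1, agrees with these values to within 0.0003.

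**Step 4. Place the trial in the range.** The documents give no correlation. A participant who falls below F-VASI75 has necessarily lost F-VASI90, so the event sets are nested and a positive correlation is expected. The 9.75% is therefore an upper bound and not a forecast. If only one of the two nulls is true, the ungated error is 5%.

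**The case against.** The strongest reply is that the inflation belongs to neither document. The protocol gates the key secondary, and the SAP claims nothing at 0.05. Moving from confirmatory to exploratory narrows what may be said, and SAP 3.2 is explicit, later than the protocol, and under the right heading. With no power calculation in either document, an exploratory stance is also natural.

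Much of this stands. The error figures are conditional on a reading that the SAP does not authorise, and the SAP's own wording is clear. It does not remove the contradiction. Protocol 10.1 has no power calculation either, and 10.3 still prescribes formal tests; a trial can control type I error without being powered. Nothing says that the SAP overrides Amendment 2: SAP 1 presents it as giving detail on analyses the protocol outlines. Nor does the SAP say that its p-values are nominal.

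On timing, SAP 9 places the primary analysis after the primary database lock and uses the future tense, and protocol 6.3 puts unblinding after that lock. Together these suggest that the SAP preceded unblinding. Against that, SAP 5.3 and 10.1 describe the Site 710 removal in the past tense, and no lock date is given. The question stays open, and nothing in the documents shows that the rule was changed after unblinding.

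**Conclusion.** The concern holds and must be fixed. SAP 3.2 states a rule that contradicts protocol 10.3 for the primary and key secondary endpoints, and SAP 10.1 omits the departure. That conclusion rests on the text alone and needs no assumption.

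The numerical consequence is conditional: 5.0% to 9.75% family-wise error in place of 5%, if both tests are read at two-sided 0.05 without the gate, both nulls are true and the statistics are bivariate normal. Kaplan-Meier estimates, log-rank statistics and hazard ratios are the same under either rule.

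**What to change.** Preferred: amend SAP 3.2 to carry the protocol's sequence. Test time to relapse at two-sided 0.05; only if it is rejected, test time to maintain F-VASI90 response at two-sided 0.05; report all other endpoints descriptively with 95% confidence intervals. Repeat the gate in SAP 7.4. This holds the family-wise error at 5% or below.

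Fallback, if exploratory status is intended: keep SAP 3.2, and add an entry to SAP 10.1 giving the reason, the date of the decision, and its timing relative to the primary database lock and unblinding. State that both log-rank p-values are nominal and that no claim of significance will be made from either.

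Under either route the amendment should be dated against the lock. If the lock has already passed, the discrepancy and its history should also be disclosed in the clinical study report.

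The cost is a short amendment to a SAP that so far has one version. The fixed sequence takes no alpha from the primary, needs no further participants and alters no estimate.
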